6.3.1 Withdrawal from Treatment

The patient must be withdrawn from treatment with Pan-HER in the event of any of the following:

- A DLT considered by the Investigator to require treatment discontinuation (Part 1 only) (See **Section 9.5**)
- Occurrence of an AE considered by the Investigator to require treatment discontinuation
- Need for more than three dose-reductions of Pan-HER
- Patients with hepatotoxicity that cannot be explained by factors not related to Pan-HER, i.e., Hy's Law criteria (24)

Note: Patients meeting all three of the following are considered to have met Hy's Law criteria:

- Hepatocellular injury, generally shown by a higher incidence of 3-fold or greater elevations above ULN of ALT or AST (or > 3 × baseline if elevated at study entry due to hepatic involvement by tumor).
- Elevation of serum total bilirubin to $\ge 2 \times ULN$, without findings of cholestasis (elevated serum alkaline phosphatase [ALP] $< 2 \times ULN$).
- No other reason to explain the combination of increased aminotransferase and serum total bilirubin, such as viral hepatitis A, B, or C; preexisting or acute liver disease; or another drug capable of causing the observed injury.
- PD, verified by CT/MRI according to RECIST v1.1
- Treatment failure not meeting the criteria for PD, but considered by the Investigator to require treatment discontinuation
- Requirement for a significant surgical procedure

Note: Patients requiring a minor surgical procedure (e.g., port placement, skin abscess drainage) may continue at the Investigator's discretion following discussion with the Sponsor or designee. A brief interruption in therapy may be considered.

Confidential Page 52 of 156

- An intercurrent illness which, in the opinion of the Investigator, would prevent completion of trial-related evaluations
- Use of prohibited concomitant medication, as defined in **Section 7.5.2**
- Pregnancy
- Significant deviation from the eligibility criteria may require discontinuation after discussion with the Sponsor
- Noncompliance with trial procedures may require discontinuation after discussion with the Sponsor
- Patient election to discontinue treatment
- Termination of the trial by the Sponsor

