7.1.4.3 Dose-Reduction for Pan-HER-Related Toxicities

Patients experiencing any of the following toxicities, assessed as possibly, probably, or related to Pan-HER, will have their dose reduced in accordance with the reduction schedule outlined in **Table 9**:

- 1. Grade 3 non-hematologic toxicity regardless of duration, with the exception of:
 - a. Grade 3 nausea, vomiting, diarrhea, or fatigue lasting ≤2 days with best supportive care
 - b. Grade 3 asymptomatic electrolyte abnormality that is not considered clinically significant by the Investigator and that is controlled with medical therapy
- 2. Grade 4 non-hematologic toxicity, with the exception of:
 - a. Grade 4 asymptomatic electrolyte abnormalities that is not considered clinically significant by the Investigator and that is controlled with medical therapy
- 3. Neutropenia that is:
 - a. Grade 3-4 febrile neutropenia
 - b. Grade 4 and sustained (i.e., ANC $< 0.5 \times 10^9 / L [500 / mm^3]$, duration > 5 days)
- 4. Thrombocytopenia that is
 - a. Grade 3 with clinically significant hemorrhage
 - b. Grade 4 (platelets $<25 \times 10^9/L$ [25,000/mm³])
- 5. AST/ALT elevation >3×ULN (or >3× baseline if elevated at study entry due to hepatic involvement by tumor) with bilirubin elevation >2×ULN without evidence of cholestasis that cannot be explained by factors not related to Pan-HER
- 6. Evidence of cardiac toxicity as defined by either:
 - a. ≥16% absolute decrease in LVEF from baseline, or
 - b. LVEF below the institutional lower limit of normal and ≥10% absolute decrease in LVEF from baseline

Need for more than three dose-reductions of Pan-HER will lead to withdrawal from treatment.

Confidential Page 65 of 156

Table 9	Pan_HER	Dose-Reduction	n Schedule
1 41711 /			,,,,,,,,,,,,,,,,,,,,,,,,,,,,,,,,,,,,,,,

Dose Level	First Reduction	Second Reduction	Third Reduction
Dose level 1 1.0 mg/kg	0.5 mg/kg	0.25 mg/kg	0.125 mg/kg
Dose level 2	1 mg/kg	0.5 mg/kg	0.25 mg/kg
Dose level 3	Dose level 2	1 mg/kg	0.5 mg/kg
Dose level 4	Dose level 3	Dose level 2	1 mg/kg
Continue as above	Next lower tolerated dose	Next lower tolerated dose	Next lower tolerated dose

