9.2.3 Intensity

All referenced toxicity grading within this protocol will be according to the CTCAE v4.03. If the severity of an AE is not specifically graded by the CTCAE guidance document, the Investigator should use the general definitions of Grades 1 to 5 as per the following, and use his/her best medical judgment to describe the severity of the AE:

• Grade 1: Mild

Confidential Page 88 of 156

- Grade 2: Moderate
- Grade 3: Severe
- Grade 4: Life-threatening or disabling
- Grade 5: Death caused by the event

Changes in severity of AEs will be recorded.

Generally, an AE of Grade 4 or 5 qualifies for SAE reporting to the Sponsor or designee; however, the definition of Grade 4 does not necessarily always meet the regulatory definition of "life-threatening". As an example, a laboratory abnormality of Grade 4 does not need to be reported as an SAE, unless it meets one of the seriousness criteria in **Section 9.1.4**.

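### A related Hy's Law case must be withdrawn under Protocol 6.3.1 but dose-reduced under 7.1.4.3, and no section states which rule prevails

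*Protocol*

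**What the plan says.** **Withdrawal (Protocol 6.3.1).** The list opens with "The patient must be withdrawn from treatment with Pan-HER in the event of any of the following". One entry reads "Patients with hepatotoxicity that cannot be explained by factors not related to Pan-HER" and ties this to Hy's Law. Three conditions must all hold:
- ALT or AST at least three times ULN, or more than three times baseline if raised at entry by liver involvement.
- Total bilirubin at least 2×ULN, "without findings of cholestasis (elevated serum alkaline phosphatase [ALP" being below 2×ULN.
- No other explanation.

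This entry leaves nothing to investigator judgment, whereas the DLT and general AE entries in the same list do.

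**Dose reduction (Protocol 7.1.4.3).** Patients with a listed toxicity rated possibly related, probably related or related "will have their dose reduced in accordance with the reduction schedule outlined in" Table 9. Three items matter here:
- Item 5: "AST/ALT elevation >3×ULN (or >3× baseline if elevated at study entry due to hepatic involvement by tumor) with bilirubin elevation >2×ULN", with no evidence of cholestasis and no non-Pan-HER explanation.
- Item 1: "Grade 3 non-hematologic toxicity regardless of duration, with the exception of" short-lived nausea, vomiting, diarrhea or fatigue, and certain electrolyte abnormalities.
- Item 2: "Grade 4 non-hematologic toxicity, with the exception of" certain electrolyte abnormalities.

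No exception covers liver tests. The only link from 7.1.4.3 to withdrawal is the need for more than three reductions.

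**The concern.** Two mandatory instructions give opposite actions for the same patient. One ends treatment. The other continues it at a lower dose. Neither section refers to the other.

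The stake is patient safety: re-exposure to Pan-HER after suspected drug-induced liver injury. A site that goes to the dose-modification section finds the Hy's Law pattern listed as a reason to reduce and sees no pointer to the withdrawal rule. A secondary stake is consistency. Sites could handle identical events differently, which would move patients between the SAP's descriptive summaries of discontinuations, dose reductions and relative dose intensity (SAP 4.9 and 4.11.2).

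**Working it through.** The plan gives no figure to reproduce, so the check compares the two rules.

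**1. Thresholds side by side** (×ULN, normal liver tests at entry)

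| Condition | 6.3.1: withdraw | 7.1.4.3 item 5: reduce |
|---|---|---|
| ALT/AST | ≥3 | >3 |
| Bilirubin | ≥2 | >2 |
| Cholestasis | none, tied to ALP <2 | none, not further defined |
| Other cause | none | none |
| Relatedness | no separate rating | at least possibly related |

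If the 6.3.1 meaning of cholestasis is carried into item 5, every patient who meets item 5 also meets 6.3.1. The two limits of >3 and >2 lie inside ≥3 and ≥2, and the other conditions are the same or narrower.

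**2. The Grade 3–4 route.** Protocol 9.2.3 states: "All referenced toxicity grading within this protocol will be according to the CTCAE v4.03". SAP 7.4 applies that version and starts Grade 3 above 5×ULN for AST/ALT and above 3×ULN for bilirubin. The more severe Hy's Law cases therefore also meet item 1 or item 2.

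**3. Example profiles** (ALP normal, no other cause, possibly related)

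| ALT | Bilirubin | 6.3.1 | 7.1.4.3 |
|---|---|---|---|
| 4 | 2.5 | withdraw | reduce (item 5) |
| 6 | 3.5 | withdraw | reduce (items 1 and 5) |
| 6 | 2.0 | withdraw | reduce (item 1 only) |
| 3.0 | 2.5 | withdraw | none |
| 4 | 2.0 | withdraw | none |

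The first three rows conflict. The last two are the equality cases: item 5 uses strict inequalities and nothing reaches Grade 3, so only withdrawal applies. The third row shows that deleting item 5 alone would not remove every conflict.

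**4. Search for a precedence rule**
- Protocol 5.3.3 has patients treated at the allocated dose until withdrawal and says reductions may be required.
- Protocol 7.1.4 introduces reductions in similar terms.
- Protocol 7.1.4.2 delays dosing until the retreatment criteria are met. That postpones the next dose but does not forbid it.
- SAP 3.2.4.1 repeats the DLT definition and adds no handling rule.

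None of these ranks 6.3.1 against 7.1.4.3.

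**5. Size for one patient.** Reductions go to the next lower tolerated dose. Assuming the next lower planned level was tolerated:
- 9 to 6 mg/kg: 6/9 = 66.7% of the prior dose
- 12 to 9 mg/kg: 9/12 = 75.0%
- 15 to 12 mg/kg: 12/15 = 80.0%

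Under 6.3.1 the figure is 0%.

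**6. Frequency.** Protocol 3.2.4.1 summarizes 19 patients and mentions no Hy's Law case. If that silence is taken as 0 of 19, the exact 95% upper limit is 1 − 0.025^(1/19) = 17.6%. The summary does not say that patients were screened for the pattern, and it describes the data as not fully verified, so this is a loose bound.

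**7. DLT status.** A Cycle 1 event meeting 9.5.1 item 5 is a DLT whether the patient is then withdrawn or reduced. A patient who leaves Cycle 1 because of drug toxicity stays in the DLT Analysis Set (Protocol 10.2, SAP 4.5). DLT counts and the MTD are therefore the same under either rule.

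**The case against.** The strongest reply is that withdrawal plainly governs. The 6.3.1 wording is absolute, a withdrawn patient has no next dose to reduce, and 5.3.3 places reductions within the treatment period. A site that re-doses breaches 6.3.1, whereas a site that withdraws leaves 7.1.4.3 nothing to act on. Table 8 supports this reading: it stops treatment after a Grade 4 infusion-related reaction, although item 2 read literally would call for a reduction. Specific stop rules appear to sit above a general reduction list.

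That is a sensible reading, and it limits the risk. It remains an inference. Section 7.1.4.3 does mention withdrawal, but only for more than three reductions, and it names the Hy's Law pattern as a trigger for reduction. Item 5 is not leftover text either: the Amendment 5 log shows the same baseline alternative being added to both 6.3.1 and item 5. Where the sponsor wanted a choice between stopping and reducing, as for a Grade 3 infusion-related reaction in Table 8, it wrote one.

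A second reply is that other safeguards apply. Dosing is held until the retreatment criteria are met, and a Cycle 1 DLT must be reported to the sponsor within 24 hours (9.5.3). This stands, and it narrows the concern to re-dosing after recovery. It does not remove it.

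A reader might also infer that item 5 has its own role, covering patients with ALP at or above 2×ULN but no cholestasis. The documents do not support that. The only definition they give, in 6.3.1, ties absence of cholestasis to ALP below 2×ULN, so such a patient would not meet item 5 either.

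**Conclusion.** The conflict is real and should be fixed. It is a small safety-wording correction. It covers Hy's Law cases rated at least possibly related, except those exactly at 3.0×ULN for ALT/AST or 2.0×ULN for bilirubin with no value at Grade 3 or above.

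Three stronger readings do not hold:
- That every Hy's Law patient faces both rules. The equality cases above, and cases not rated as related, trigger withdrawal only.
- That the protocol directs re-dosing after liver injury. It gives both instructions, and withdrawal is the more natural one to follow.
- That dose-finding is compromised. DLT counts and the MTD are unaffected.

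The conclusion assumes that liver-test elevations count as non-hematologic toxicity for items 1 and 2, graded by the limits in SAP 7.4. The item 5 conflict does not depend on that. Practical reach is limited because the SAP introduction says enrollment stopped during Part 1. The change helps patients still being dosed, whom Protocol 5.6 allows to continue or move to a rollover protocol, and any later use of this text.

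**What to change.** 1. In the 7.1.4.3 lead-in, keep "will have their dose reduced in accordance with the reduction schedule outlined in" Table 9 and add: *unless a withdrawal criterion in Section 6.3.1 is met*. This resolves the conflict for items 1, 2 and 5 together.
2. Add to item 5: *Patients meeting Hy's Law criteria must be withdrawn; see Section 6.3.1.* Alternatively, delete item 5, since under the 6.3.1 definition of cholestasis it is essentially contained in the withdrawal rule. The lead-in clause is needed either way, because items 1 and 2 still catch Grade 3–4 liver tests.
3. Leave the DLT definition in Protocol 9.5.1 and SAP 3.2.4.1 unchanged.

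The cost is two short edits to one protocol section. Design, sample size, data collection and the SAP are untouched.

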7.2 Other Drugs to be Used in the Trial

7.2.1 Pre-Medication for Pan-HER Infusion-Related Reactions

There is an inherent risk for IRRs with the administration of mAbs. A premedication schedule will therefore be implemented for all patients treated.

For Part 1, premedication is mandatory prior to each dose of Pan-HER.

For Part 2, premedication is mandatory prior to each dose of Pan-HER during Cycle 1 and 2.

As of Amendment 5, all patients must be premedicated as described with standard therapies that include each of the following. The recommended premedication doses are as follows:

- Montelukast (selective leukotriene receptor antagonist) 10 mg PO daily × 7 prior to each Pan-HER infusion (schedule may be extended to daily throughout study at the Investigator's discretion); plus approx. 0.5 hours prior to the start of Pan-HER infusion
- Dexamethasone 10 mg PO, approx. 12 and 6 hours prior to the start of Pan-HER infusion
- Glucocorticoid therapy equivalent to 80-100 mg IV methylprednisolone, approx. 0.5 to 2 hours prior to the start of Pan-HER infusion
- Antihistamine (H1 antagonist) equivalent to 25-50 mg IV diphenhydramine, approx. 0.5 hours prior to the start of Pan-HER infusion
- Antihistamine (H2) antagonist such as 50 mg IV ranitidine or 30 mg famotidine, approx. 0.5 hours prior to the start of Pan-HER infusion

Confidential Page 66 of 156

 Acetaminophen such as 1000 mg IV or PO (orally), approx. 0.5 hours prior to the start of Pan-HER infusion

In Part 2, if a patient is without evidence of IRRs after Cycle 2, the Investigator may choose to withdraw premedication on a patient-by-patient basis with subsequent dosing in order to determine whether such continued therapy is necessary in that patient. Where practical, it is recommended that withdrawal of premedication be done in a gradual fashion.

For those patients who experienced symptoms suggestive of an IRR after Cycle 1, consideration should be given to continuing premedication for at minimum 1 to 2 additional doses before any future attempt to withdraw.

7.2.2 Treatment of Toxicities (Other Than IRRs)

7.2.2.1 Mandatory Prophylactic Treatment

Oropharyngeal Mucositis

As of Amendment 5, for prophylaxis against Pan-HER-associated oropharyngeal mucositis, the following management is mandatory throughout the Pan-HER treatment period during Part 1, and throughout the Cycle 1 and 2 Pan-HER treatment period during Part 2:

- Use of alcohol-free dexamethasone-containing oral solution; recommended 10 mL containing 0.5 mg/5 mL dexamethasone, 4× per day (swish/gargle for approximately 2 minutes then spit)
- Avoidance of alcohol- or peroxide-containing mouthwashes
- In addition, patients to be provided with instructions by the site on how best to prevent and manage oral symptoms, including but not limited to instruction to rinse mouth frequently with water (may add salt or baking-soda), use saliva substitutes if needed, apply lip moisturizer, maintain good oral hygiene, dietary restrictions, etc.

In Part 2, if a patient is without evidence of mucositis after Cycle 2, the Investigator may choose to withdraw prophylaxis on a patient-by-patient basis with subsequent dosing to determine whether such continued therapy is necessary in that patient. Where practical, it is recommended that withdrawal of prophylactic therapy be done in a gradual fashion.

Other Toxicities

Mandatory prophylactic treatment will be implemented for all patients treated in this trial should an increased incidence begin to occur of other mild-to-moderate Pan-HER-related reactions that

Confidential Page 67 of 156

are amenable to prophylaxis with standard agents. Such actions will occur following discussions within the SMC.

7.2.2.2 Therapeutic Treatment

Oropharyngeal Mucositis

As of Amendment 5, in the event of development of Pan-HER-associated oropharyngeal mucositis, appropriate standard supportive care measures are to be implemented and should include:

- Application of topical or local analgesic agents such as oral benzocaine preparations
- Protective barrier-based combination mouthwash (e.g., Magic Mouthwash or similar preparation)
- Hydration, nutritional support, as needed
- Systemic analgesia, as needed
- Antibiotic, antifungal, antiviral support, as needed
- Other methods of support, per institutional standards

Cardiac Toxicity

Recent studies administering anti-HER2 drugs have confirmed the potential for cardiac toxicity, specifically dilated cardiomyopathy. Patients will be scheduled for an ECHO at screening to exclude enrollment of patients with insufficient LVEF; alternatively, a MUGA scan of the heart can be performed. Follow-up cardiac evaluations will also be performed at the EOT visit.

In the event of cardiac symptoms (e.g., shortness of breath, edemas) an electrocardiogram (ECG) and an ECHO or MUGA is to be performed as soon as possible to ensure clinically relevant cardiac AEs are detected, including but not limited to left ventricular systolic dysfunction and LVEF decrease.

Gastrointestinal Toxicity

Recent studies with anti-HER drugs have confirmed the potential for gastrointestinal toxicity, including diarrhea, stomatitis, nausea and vomiting. Appropriate standard supportive care measures are recommended for symptomatic patients.

Confidential Page 68 of 156

Integument Toxicity

AEs of skin and subcutaneous tissues are a hallmark of anti-EGFR drugs and, to a lesser degree, of anti-HER2/HER3 drugs. The toxicity studies in cynomolgus monkeys have revealed limited signs of skin toxicity. Therefore, it is considered appropriate to remain reactive to symptoms with standard supportive care measures; however, preemptive skin care measures or treatment (including, topical or oral antibiotics and corticosteroids) remain at the Investigator's discretion.

Fatigue

Recent studies with anti-HER3 drugs have revealed the potential of chronic fatigue following administration. A causal treatment of chronic fatigue is unknown and therefore a treatment program managing the physical and emotional effects of chronic fatigue symptoms should be considered at the Investigator's discretion.

Other Potential Toxicities

Recent studies with anti-HER drugs have revealed further potential toxicities as listed below:

- Hepatotoxicity
 - Regular serum chemistry samples will be analyzed to address potential increase in liver function tests
- Pulmonary tissue toxicity
 - It is considered appropriate to remain reactive, e.g., symptomatic patients should be scheduled for thoracic X-ray or thoracic CT to address potential interstitial lung disease or acute interstitial pneumonitis
- Metabolic deteriorations
 - Regular blood samples will be analyzed to assess hyperglycemia, hypomagnesemia, and hypokalemia
- Musculoskeletal and connective tissue disorders
 - o It is considered appropriate to remain reactive, e.g., joint pain requiring supportive care measures

7.3 Blinding

Not applicable.

Confidential Page 69 of 156

7.4 Drug Accountability and Compliance Check

The Investigator is responsible for ensuring accountability for the IMP, including maintenance of IMP accountability records.

IMP accountability records will include a full inventory of the IMP including:

- Confirmation of IMP delivery to the trial site
- Record of each dose dispensed
- The return of unused IMP to the Sponsor or designee
- Record of any on-site destruction of unused IMP, as agreed with the Sponsor or designee

Records will specify dates, quantities, batch numbers, use-by dates and patient numbers, as applicable.

The Investigator, or designee, should maintain records that adequately document:

- That the patients were provided the doses specified by the protocol, and
- That all IMP provided by the Sponsor was fully reconciled

7.5 Concomitant Medication/Therapy

7.5.1 Allowed Medication/Therapy and Procedures During the Trial

Patients may receive their current concomitant medication and any medication considered necessary for the welfare of the patient during trial, except if listed in **Section 7.5.2**.

Furthermore, the following are permitted during the trial:

- Premedication with standard therapies prior to Pan-HER administration to reduce the risk of IRRs
- Prophylaxis and treatment of Pan-HER-related toxicities
- Radiotherapy for pain control against non-target lesions, as long as it does not influence bone marrow function

7.5.2 Prohibited Medication/Therapy and Procedures During the Trial

The following medications and procedures are not allowed from C1/D1, or as specified in the inclusion/exclusion criteria, until the EOT Visit:

• Anti-cancer treatment, including cytotoxic or cytostatic agents, hormonal therapy (except as physiologic hormone replacement) and EGFR/HER-targeting therapies

Confidential Page 70 of 156

- Radiotherapy against target lesion(s) (Part 2 only)
- Systemic immunosuppressive or systemic hormonal therapy (> 10 mg daily prednisone equivalent) with the exception of the following allowed therapies:
 - o Hormonal therapy (e.g., Megace) for appetite stimulation
 - o Nasal, ophthalmic, inhaled, and topical glucocorticoid preparations
 - o Hormone replacement therapy at standard doses for end-organ failure
 - Steroid therapy as prophylaxis for contrast reactions
 - o Intra-articular steroid injections
 - Hormonal therapy for ovarian suppression, hormonal contraceptive therapy, postmenopausal HRT
 - o GnRH analogs in patients with prostate cancer
 - Low-dose maintenance steroid therapy for other conditions (excluding steroid tapers for brain edema/metastases/radiation)
 - Higher dose steroid therapy for treatment of an acute intercurrent illness in patients with stable disease or an ongoing response. In such situations, study drug treatment should be interrupted for the duration of immunosuppressive therapy
- Prophylactic use of hematopoietic growth factors during Cycle 1
- Use of alcohol- or peroxide-containing mouthwashes
- Major surgery that would preclude the patient from complying with the requirements of the protocol

If any one of the above listed medications/procedures becomes necessary during the trial, the patient must be withdrawn from Pan-HER and the EOT Visit should be performed. The 1M FUP Visit should then be performed, no less than 1 month (30+7 days) after the last dose of Pan-HER.

